APPENDIX C. CLINICALLY NOTABLE EVENTS BASED ON CUSTOMIZED MEDDRA QUERIES

This appendix provides the categories of clinically notable events based on customized MQs.

Clinically Notable Hematological Events

Category	Preferred Term
Anemia	Anaemia macrocytic
Anemia	Aplasia pure red cell
Anemia	Aplastic anaemia
Anemia	Erythroblast count decreased
Anemia	Erythropenia
Anemia	Hypoplastic anaemia
Anemia	Microcytic anaemia
Anemia	Red blood cell count decreased
Anemia	Anaemia
Anemia	Haematocrit decreased
Anemia	Haemoglobin decreased
Anemia	Leukoerythroblastic anaemia
Neutropenia	Agranulocytosis
Neutropenia	Band neutrophil count decreased
Neutropenia	Febrile neutropenia
Neutropenia	Granulocyte count decreased
Neutropenia	Granulocytopenia
Neutropenia	Neutropenia
Neutropenia	Neutropenic infection
Neutropenia	Neutropenic sepsis
Neutropenia	Neutrophil count decreased
Thrombocytopenia	Acquired amegakaryocytic thrombocytopenia
Thrombocytopenia	Platelet count decreased
Thrombocytopenia	Thrombocytopenia
Thrombocytopenia	Plateletcrit decreased

Hematological Infection

Category	Preferred Term
EBV infection	Epstein Barr virus positive mucocutaneous ulcer
EBV infection	Epstein-Barr viraemia
EBV infection	Epstein-Barr virus associated lymphoma
EBV infection	Epstein-Barr virus associated lymphoproliferative disorder
EBV infection	Epstein-Barr virus infection
EBV infection	Hepatitis infectious mononucleosis
EBV infection	Infectious mononucleosis
EBV infection	Oral hairy leukoplakia
EBV infection	Post transplant lymphoproliferative disorder
EBV infection	X-linked lymphoproliferative syndrome
EBV infection	Epstein-Barr virus test positive
EBV infection	Epstein-Barr virus antibody positive
Cytomegaloviral infections	Congenital cytomegalovirus infection
Cytomegaloviral infections	Cytomegalovirus chorioretinitis
Cytomegaloviral infections	Cytomegalovirus colitis
Cytomegaloviral infections	Cytomegalovirus duodenitis
Cytomegaloviral infections	Cytomegalovirus enteritis
Cytomegaloviral infections	Cytomegalovirus enterocolitis
Cytomegaloviral infections	Cytomegalovirus gastritis
Cytomegaloviral infections	Cytomegalovirus gastroenteritis
Cytomegaloviral infections	Cytomegalovirus gastrointestinal infection
Cytomegaloviral infections	Cytomegalovirus gastrointestinal ulcer
Cytomegaloviral infections	Cytomegalovirus hepatitis
Cytomegaloviral infections	Cytomegalovirus infection
Cytomegaloviral infections	Cytomegalovirus mononucleosis
Cytomegaloviral infections	Cytomegalovirus mucocutaneous ulcer
Cytomegaloviral infections	Cytomegalovirus myelomeningoradiculitis
Cytomegaloviral infections	Cytomegalovirus myocarditis
Cytomegaloviral infections	Cytomegalovirus nephritis
Cytomegaloviral infections	Cytomegalovirus oesophagitis
Cytomegaloviral infections	Cytomegalovirus pancreatitis
Cytomegaloviral infections	Cytomegalovirus pericarditis
Cytomegaloviral infections	Cytomegalovirus syndrome
Cytomegaloviral infections	Cytomegalovirus urinary tract infection
Cytomegaloviral infections	Cytomegalovirus viraemia
Cytomegaloviral infections	Encephalitis cytomegalovirus
Cytomegaloviral infections	Disseminated cytomegaloviral infection
Cytomegaloviral infections	Pneumonia cytomegaloviral
Cytomegaloviral infections	Cytomegalovirus test positive

Hyperlipidemia

Category	Preferred Term
Hyperlipidemia	Acquired lipoatrophic diabetes
Hyperlipidemia	Acquired mixed hyperlipidaemia
Hyperlipidemia	Apolipoprotein B/Apolipoprotein A-1 ratio increased
Hyperlipidemia	Autoimmune hyperlipidaemia
Hyperlipidemia	Blood cholesterol abnormal
Hyperlipidemia	Blood cholesterol esterase increased
Hyperlipidemia	Blood cholesterol increased
Hyperlipidemia	Blood triglycerides abnormal
Hyperlipidemia	Blood triglycerides increased
Hyperlipidemia	Diabetic dyslipidaemia
Hyperlipidemia	Dyslipidaemia
Hyperlipidemia	High density lipoprotein abnormal
Hyperlipidemia	High density lipoprotein decreased
Hyperlipidemia	Hypercholesterolaemia
Hyperlipidemia	Hyperlipidaemia
Hyperlipidemia	Hypertriglyceridaemia
Hyperlipidemia	Hypo HDL cholesterolaemia
Hyperlipidemia	Intermediate density lipoprotein increased
Hyperlipidemia	LDL/HDL ratio increased
Hyperlipidemia	Lipids abnormal
Hyperlipidemia	Lipids increased
Hyperlipidemia	Lipoprotein (a) abnormal
Hyperlipidemia	Lipoprotein (a) increased
Hyperlipidemia	Lipoprotein abnormal
Hyperlipidemia	Lipoprotein increased
Hyperlipidemia	Low density lipoprotein abnormal
Hyperlipidemia	Low density lipoprotein increased
Hyperlipidemia	Non-high-density lipoprotein cholesterol increased
Hyperlipidemia	Remnant-like lipoprotein particles increased
Hyperlipidemia	Total cholesterol/HDL ratio abnormal
Hyperlipidemia	Total cholesterol/HDL ratio increased
Hyperlipidemia	Very low density lipoprotein abnormal
Hyperlipidemia	Very low density lipoprotein increased

QT Prolongation

Category	Preferred Term
QT prolongation	Electrocardiogram QT interval abnormal
QT prolongation	Electrocardiogram QT prolonged
QT prolongation	Long QT syndrome
QT prolongation	Long QT syndrome congenital
QT prolongation	Torsade de pointes
QT prolongation	Ventricular tachycardia

APPENDIX D. VARIOUS UPPER EFFICACY BOUNDARIES FOR TESTING DAY 28 ORR AT BOTH INTERIM 2 AND FINAL ANALYSES USING HWANG-SHIH-DECANI ALPHA SPENDING FUNCTION WITH SHAPE PARAMETER -4

No. of Subjects in the Interim 2 Efficacy Analysis Set	Information Fraction at IA2 (Column 1/436)	Efficacy Boundary/Critical Value at Interim 2 (as Compared With Observed Normalized Test Statistic z)	Final Critical Value
410	0.940367	2.062174	2.036718
411	0.942661	2.058304	2.037092
412	0.944954	2.054429	2.037452
413	0.947248	2.050549	2.037794
414	0.949541	2.046665	2.038117
415	0.951835	2.042776	2.038417
416	0.954128	2.038882	2.038691
417	0.956422	2.034984	2.038935
418	0.958716	2.03108	2.039144
419	0.961009	2.027172	2.039312
420	0.963303	2.023259	2.039433
421	0.965596	2.019341	2.039498
422	0.96789	2.015418	2.039497
423	0.970183	2.01149	2.039418
424	0.972477	2.007557	2.039247
425	0.974771	2.003619	2.038963
426	0.977064	1.999677	2.038541
427	0.979358	1.995729	2.037951
428	0.981651	1.991776	2.037147
429	0.983945	1.987817	2.036068
430	0.986239	1.983854	2.034627
431	0.988532	1.979885	2.03269
431	0.990826	1.975912	2.030039
433	0.993119	1.971933	2.026284
434	0.995413	1.967948	2.020608
435	0.997706	1.963959	2.010698

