### **5.4.2. Criteria and Procedures for Dose Interruptions and Adjustments of Study Drug**

Treatment with itacitinib/placebo may be delayed up to 14 days to allow for resolution of toxicity. After interruption, subjects should be evaluated on a weekly basis until resolution/improvement of the AE. Subjects may resume treatment if no medical condition or other circumstance exists that, in the opinion of the investigator, would make the subject unsuitable for further participation in the study. The investigator should contact the medical monitor to discuss cases where treatment has been delayed for more than 14 days before restarting treatment.

Because subjects may enter the study with compromised bone marrow function, these dose reductions are provided as guidelines (see [Table 1](#) and [Table 2](#)); individual decisions regarding dose reduction should be made using clinical judgment and an individual benefit/risk assessment, taking into account relatedness of the AE to the study drug and the subject's underlying condition. Adverse events that have a clear alternative explanation or transient ( $\leq 72$  hours) abnormal laboratory values without associated clinically significant signs or symptoms may be exempt from dose-reduction rules. The sponsor's medical monitor may be consulted for advice.

Subjects receiving itacitinib/placebo at a dose of 200 mg QD may have their dose reduced to 100 mg QD. Subjects who are unable to tolerate itacitinib/placebo at a dose of 100 mg QD should be withdrawn from study treatment.

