#### **8.1.2. Reporting**

Adverse events that begin or worsen after informed consent should be recorded on the Adverse Events form of the eCRF. Conditions that were already present at the time of informed consent should be recorded on the Medical History form in the eCRF. Monitoring for the occurrence of new AEs should be continued for at least 30 days after the last dose of study drug. Adverse events (including laboratory abnormalities that constitute AEs) should be described using a diagnosis whenever possible rather than by individual underlying signs and symptoms. When a clear diagnosis cannot be identified, each sign or symptom should be reported as a separate AE.

The term "disease progression" should be recorded as an AE/SAE itself only if there are no other identifiable AEs/SAEs associated with the disease progression at the time of reporting. For events associated with disease progression, the relevant signs and symptoms should be reported using a diagnosis whenever possible, rather than the individual underlying signs and symptoms. When a clear diagnosis cannot be identified, each sign or symptom should be reported as a separate AE. If the events resulting from disease progression meet the criteria for an SAE (eg, resulted in hospitalization, a life-threatening event, or death), the specific event(s) should be reported as an SAE(s) as described in Section 8.3.2. In both cases (ie, AEs or SAEs related to disease progression), for each event it should be indicated whether the event (diagnosis or signs and symptoms) is related to disease progression.

The severity of AEs will be assessed using CTCAE v4.03 Grades 1 through 5. If an event is not classified by CTCAE, the severity of the AE will be graded according to the scale below to estimate the grade of severity.

Grade 1	Mild; asymptomatic or mild symptoms; clinical or diagnostic observations only; intervention not indicated.
Grade 2	Moderate; minimal, local, or noninvasive intervention indicated; limiting age-appropriate activities of daily living.
Grade 3	Severe or medically significant but not immediately life-threatening; hospitalization or prolongation of hospitalization indicated; disabling; limiting self-care activities of daily living.
Grade 4	Life-threatening consequences; urgent intervention indicated.
Grade 5	Death due to AE

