## **8.2. Laboratory Test Abnormalities**

Laboratory abnormalities that constitute an AE in their own right (considered clinically meaningful, induce clinical signs or symptoms, require concomitant therapy, or require changes in study drug) should be recorded on the Adverse Event form in the eCRF. Whenever possible, a diagnosis rather than a symptom should be provided (eg, "anemia" instead of "low hemoglobin"). Laboratory abnormalities that meet the criteria for AEs should be followed until they have returned to normal or an adequate explanation of the abnormality is found. When an abnormal laboratory test result corresponds to a sign or symptom of a previously reported AE, it is not necessary to separately record the laboratory test result as an additional event.

Laboratory abnormalities that do not meet the definition of an AE should not be reported as AEs. A Grade 3 or 4 AE does not automatically indicate an SAE unless it meets the definition of serious, as defined in Section 8.3.1, and/or per the investigator's discretion. A dose modification for the laboratory abnormality may be required (see Section 5.4.2) and should not contribute to the designation of a laboratory test abnormality as an SAE.

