- Number (%) of subjects reporting TEAEs leading to itacitinib/placebo dose reduction by SOC and PT
- Number (%) of subjects reporting TEAEs leading to discontinuation of itacitinib/placebo by SOC and PT
- Number (%) of subjects reporting corticosteroid treatment-related TEAEs by SOC and PT
- Number (%) of subjects reporting corticosteroid treatment-related TEAEs by PT in decreasing order of frequency
- Number (%) of subjects reporting corticosteroid treatment-related TEAEs by SOC, PT, and highest grade
- Number (%) of subjects reporting corticosteroid treatment-related Grade 3 or higher TEAEs by SOC and PT
- Number (%) of subjects reporting corticosteroid treatment-related serious TEAEs by SOC and PT
- Number (%) of subjects reporting TEAEs leading to corticosteroid dose interruption by SOC and PT
- Number (%) of subjects reporting TEAEs leading to corticosteroid dose reduction by SOC and PT
- Number (%) of subjects reporting TEAEs leading to discontinuation of corticosteroids by SOC and PT
- Number (%) of subjects reporting TEAEs leading to withdrawal from the study by SOC and PT

The following summaries will be produced for TEAEs occurring in the treatment phase by MedDRA term based on baseline hepatic impairment status in combination with postbaseline azole usage:

- Number (%) of subjects reporting serious TEAEs by SOC and PT
- Number (%) of subjects reporting Grade 3 or higher TEAEs by SOC and PT
- Number (%) of subjects reporting fatal TEAEs by SOC and PT
- Number (%) of subjects reporting itacitinib/placebo treatment-related TEAEs by SOC and PT
- Number (%) of subjects reporting Grade 3 or higher thrombocytopenia TEAEs by SOC and PT based on customized MQ
- Number (%) of subjects reporting Grade 3 or higher neutropenia TEAEs by SOC and PT based on customized MQ
- Number (%) of subjects reporting Grade 3 or higher anemia TEAEs by SOC and PT based on customized MQ

Severity of hepatic impairment at baseline is defined as follows:

- Normal: Total bilirubin \leq ULN and AST \leq ULN
- Mild: Total bilirubin > 1.0 to $1.5 \times$ ULN and AST = any value or total bilirubin \leq ULN and AST $>$ ULN
- Moderate: Total bilirubin > 1.5 to $3 \times$ ULN and AST = any value
- Severe: Total bilirubin $> 3.0 \times$ ULN and AST = any value

If multiple azoles were used postbaseline, the most potent azole will be used for classification according to the following potency order (listed from strongest to weakest):

1. Ketoconazole
2. Itraconazole
3. Voriconazole

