8.3. Clinically Notable Treatment-Emergent Adverse Events Based on Customized MedDRA Queries

The following categories of clinically notable events will be summarized based on customized MQs (see [Appendix C](#)):

- Anemia
- Neutropenia
- Thrombocytopenia
- QT prolongation
- Hyperlipidemia
- EBV infection
- CMV infection

Within each category, the number and percentage of subjects with at least 1 TEAE occurring during the treatment phase tabulated by MedDRA PT will be summarized. Summaries of clinically notable TEAEs based on customized MQs will be provided by treatment group, category, PT, and the highest grade or outcome.

- Overall summary of clinically notable TEAEs in the treatment phase based on customized MQs
- Number (%) of subjects with clinically notable TEAEs in the treatment phase based on customized MQs by PT and outcome
- Number (%) of subjects with clinically notable TEAEs in the treatment phase based on customized MQs by PT and highest grade

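### The SAP's anemia, neutropenia and thrombocytopenia queries omit pancytopenia and bone marrow failure and place aplastic anaemia under anemia only, so the query-based tables lack a complete count of subjects with cytopenia

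*SAP*

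**What the plan says.** SAP 8.3 names seven categories of clinically notable events. Three are cytopenias (anemia, neutropenia, thrombocytopenia), and none is multi-lineage. Within each category the SAP reports "the number and percentage of subjects with at least 1 TEAE occurring during the treatment phase", and one of the planned outputs is "Number (%) of subjects with clinically notable TEAEs in the treatment phase based on customized MQs by PT and highest grade". SAP Appendix B numbers these outputs as Tables 3.2.26-3.2.28. Appendix C supplies the term lists: "This appendix provides the categories of clinically notable events based on customized MQs".

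The same queries are used in SAP 8.2.2 for three tables broken down by baseline hepatic impairment and postbaseline azole use. The first is "Number (%) of subjects reporting Grade 3 or higher thrombocytopenia TEAEs by SOC and PT based on customized MQ", with matching tables for neutropenia and anemia (Tables 3.2.33-3.2.35).

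On recording, Protocol 8.1.2 says that adverse events "should be described using a diagnosis whenever possible rather than by individual underlying signs and symptoms". Protocol 8.2 repeats this for laboratory abnormalities: "Whenever possible, a diagnosis rather than a symptom should be provided". It adds that when an abnormal result corresponds to a sign of an event already reported, "it is not necessary to separately record the laboratory test result as an additional event".

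**The concern.** Myelosuppression is a named risk of itacitinib (Protocol 1.5), and thrombocytopenia helped settle the dose (Protocol 1.4.2). The population is post-transplant, and secondary graft failure is itself an endpoint. The Protocol expects impaired marrow at entry; it introduces its dose-reduction guidelines with "Because subjects may enter the study with compromised bone marrow function". A site that sees all three blood lines fall can reasonably record one diagnosis, pancytopenia, and under Protocol 8.2 need not add separate entries for the corresponding low counts.

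The customized queries exist to gather related terms into one subject count per lineage. If the single recorded diagnosis is outside the lists, the most general form of marrow suppression is the one the query-based tables do not count. The breakdown by azole use matters because itraconazole raised itacitinib exposure nearly 5-fold in healthy volunteers (Protocol 1.5).

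**Working it through.** The plan gives no figure to reproduce here. The check is a row count and a trace of where the lists are used.

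**Row count, SAP Appendix C, hematological events**

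| Query | Terms | Pancytopenia | Bone marrow failure | Aplastic anaemia |
|---|---|---|---|---|
| Anemia | 12 | 0 | 0 | 1 |
| Neutropenia | 9 | 0 | 0 | 0 |
| Thrombocytopenia | 4 | 0 | 0 | 0 |
| Total | 12 + 9 + 4 = 25 | 0 | 0 | 1 |

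The list shows no redaction. No other SAP text adds terms or maps one term to several lineages.

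**What happens to a subject with a single cytopenia record**

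- Pancytopenia or bone marrow failure only: counted in 0 of the 3 lineage categories.
- Aplastic anaemia only: counted in 1 of the 3 (anemia).

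**Size in Tables 3.2.26-3.2.28**

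The safety analysis set is subjects with at least one dose (SAP 5.3.4). Assume all 218 planned subjects per arm are dosed.

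- One missed subject in one category: 1/218 = 0.0046, or about 0.46 percentage points.
- Unlisted term with all three lineages low: each of three categories is lower by 0.46 points.
- Unlisted term with two lineages low: two categories are lower by 0.46 points and the third is unchanged.
- Aplastic anaemia only, with all three lineages low: neutropenia and thrombocytopenia are each lower by 0.46 points, and anemia is unchanged.

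With fewer subjects dosed, the per-subject figure rises slightly. The documents give no rate for these terms, so the number of missed subjects cannot be stated. Tables 3.2.33-3.2.35 are split by hepatic status and azole use, and their denominators are not given, so no percentage is offered for them.

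**Where the events can still be seen**

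| Source | What it shows | What it lacks |
|---|---|---|
| General tables by SOC and preferred term, such as 3.2.2 | Pancytopenia in its own row | One count across related terms |
| Table 3.2.30 | All Grade 3 or higher events by preferred term, hepatic status and azole use | The same |
| Adverse event listings | Every record | A summary count |
| Table 3.3.3 | CTC grade shift by hematology parameter, independent of adverse event coding | Hepatic and azole breakdown; a subject count across lineages |

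Preferred-term rows cannot be added to recover the missing count, because one subject may appear in several rows. The three lineage categories cannot be added either, for the same reason.

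**The case against.** The strongest reply is that this is a design choice. SAP 8.3 promises lineage categories and does not promise a measure of myelosuppression overall. A multi-lineage diagnosis carries one grade and does not say which lineage earned it, so leaving it out keeps the lineage counts specific. That is a fair reason not to place pancytopenia in all three lists. It is not a reason to have no category for it, and the lists already include a marrow-level diagnosis, aplastic anaemia, under one lineage.

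The second reply is that such a lone record may be rare. The Protocol's own example of a diagnosis is anemia, which is lineage-specific. The dose-modification rules in Protocol Table 1 treat neutrophils and platelets separately, and Protocol 8.2 only makes separate recording unnecessary; it does not forbid it. This stands: the case is foreseeable, but nothing in the Protocol requires it.

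A reader might infer that severe marrow toxicity by hepatic status and azole use would go unseen in Tables 3.2.33-3.2.35. The documents do not support that. Table 3.2.30 applies the same grade cut and the same breakdown to all events, and a Grade 3 or higher pancytopenia would have its own row there.

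A reader might also infer that the comparison between arms is biased. No rate or between-arm difference for these terms is given, so that cannot be said either.

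**Conclusion.** The gap is real and small. The query-based tables do not give a complete, de-duplicated count of subjects with cytopenia, because subjects recorded only under pancytopenia or bone marrow failure are in no lineage category, and those recorded only under aplastic anaemia are in one.

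This rests on one assumption from outside the documents: that these diagnoses code to their own preferred terms. The documents name no MedDRA version. It also depends on the subject having no separate lineage-specific event in the treatment phase.

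These are descriptive safety summaries, and no efficacy test, alpha or stopping rule is touched. The weight is the lowest minor: a cheap improvement.

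**What to change.** Before the final analysis, change Appendix C and SAP 8.3 as follows.

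- Add a separate multi-lineage cytopenia category containing pancytopenia, bone marrow failure and similar terms, with names checked against the MedDRA version in use. Include aplastic anaemia there, and also keep it under anemia so that no subject counted today drops out.
- Add an any-cytopenia row to Tables 3.2.26-3.2.28. It counts each subject once if they have an event in the anemia, neutropenia, thrombocytopenia or multi-lineage category.
- Add one Grade 3 or higher multi-lineage table by hepatic status and azole use alongside Tables 3.2.33-3.2.35.

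Do not copy the single adverse event grade into every lineage. A Grade 4 event driven by platelets would then also appear as Grade 4 anemia and Grade 4 neutropenia. Do not put laboratory grades into the adverse event lineage tables either. That would need laboratory values matched to event windows and to baseline for each lineage, and it would mix two grading sources in one table; Table 3.3.3 already reports the laboratory data.

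The cost is minor query and table work with no new data. Some subjects may also have secondary graft failure (Listing 2.6.5), and a footnote can flag that overlap. SAP Amendment 1 already revised these queries once (SAP 10.2.1), so a further edit is routine.
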